8.2.1.7. Assessment of Intensity

The investigator will make an assessment of intensity (Grade) for each AE and SAE reported during the study, using as a guide the NCI CTCAE, as provided in the Study Procedures Manual.

8.2.1.8. Follow-up of Adverse Events and Serious Adverse Events

The investigator is obligated to perform or arrange for the conduct of supplemental measurements and/or evaluations as medically indicated or as requested by CicloMed or its designee to elucidate the nature and/or causality of the AE or SAE as fully as possible. This may include additional laboratory tests or investigations, histopathological examinations, or consultation with other health care professionals.

If a patient dies during participation in the study or during a recognized follow-up period, the investigator will provide CicloMed or its designee with a copy of any post-mortem findings including histopathology.

New or updated information will be recorded in the originally completed CRF.

The investigator will submit any updated SAE data to the Sponsor within 24 hours of receipt of the information. Contacts for SAE reporting can be found in the Study Procedures Manual.

8.2.2. Pregnancy

Pregnancies in female patients and female partners of male patients will be recorded from after the start of study intervention until 30 days after the last dose. All pregnancies must be followed to conclusion to determine outcomes for both mother and baby.

While pregnancy itself is not considered to be an AE or SAE, any pregnancy complication or elective termination of a pregnancy will be reported as an AE or SAE. A spontaneous abortion is always considered to be an SAE and will be reported as such. Any post-study pregnancy-related SAE considered reasonably related to the study intervention by the investigator will be reported to the Sponsor as described in Sections [8.2.1.4](#) and [8.2.1.5](#).

While the investigator is not obligated to actively seek this information in former study patients, he or she may learn of an SAE through spontaneous reporting.

8.2.2.1. Male Patients with Partners who Become Pregnant

The investigator will attempt to collect pregnancy information on any male patient's female partner who becomes pregnant while the male patient is in this study. This applies only to male patients who receive CPX-POM.

After obtaining the necessary signed informed consent from the pregnant female partner directly, the investigator will record pregnancy information on the appropriate form and submit it to the Sponsor within 24 hours of learning of the partner's pregnancy. The female partner will also be followed to determine the outcome of the pregnancy. Information on the status of the mother and child will be forwarded to the Sponsor. Generally, the follow-up will be no longer than 6 to 8 weeks following the estimated delivery date. Any termination of the pregnancy will be reported regardless of fetal status (presence or absence of anomalies) or indication for the procedure.

8.2.2.2. Female Patients who Become Pregnant

The investigator will collect pregnancy information on any female patient who becomes pregnant while participating in this study. Information will be recorded on the appropriate form and submitted to the Sponsor within 24 hours of learning of a patient's pregnancy. The patient will be followed to determine the outcome of the pregnancy. The investigator will collect follow-up information on the patient and the neonate and the information will be forwarded to the Sponsor. Generally, follow-up will not be required for longer than 6 to 8 weeks beyond the estimated delivery date. Any termination of pregnancy will be reported, regardless of fetal status (presence or absence of anomalies) or indication for the procedure.

Any female patient who becomes pregnant while participating in the study will discontinue CPX-POM and be withdrawn from the study.

8.2.3. Other Safety and Screening Assessments

8.2.3.1. Cardiac Evaluation

Patients will undergo a cardiac evaluation at Screening using MUGA or ECHO to evaluate their eligibility to participate in the study.

Patients will also undergo a chest X-ray or CT scan to confirm normal cardiac appearance/heart size at Screening.

8.2.3.2. Eastern Cooperative Oncology Group

Patients will be evaluated for ECOG performance status at Screening and Follow-Up to evaluate their eligibility to participate in the study. The ECOG performance status grades and criteria are shown in Table 5.

Table 5. Eastern Cooperative Performance Status

| GRADE | ECOG PERFORMANCE STATUS |
|-------|---|
| 0 | Fully active, able to carry on all pre-disease performance without restriction |
| 1 | Restricted in physically strenuous activity but ambulatory and able to carry out work of a light or sedentary nature, e.g., light house work, office work |
| 2 | Ambulatory and capable of all selfcare but unable to carry out any work activities; up and about more than 50% of waking hours |
| 3 | Capable of only limited selfcare; confined to bed or chair more than 50% of waking hours |
| 4 | Completely disabled; cannot carry on any selfcare; totally confined to bed or chair |
| 5 | Dead |

8.2.3.3. Physical Examinations

A complete physical examination will be conducted at Screening and Follow-up. At each other study visit, patients will be assessed for continued dosing and any possible symptoms/toxicities and a physical examination may be performed, if indicated (see Schedule of Assessments, [Table 1]). Body weight should be measured at each study visit. Height should be measured at Screening.

8.2.3.4. Vital Signs

Vital signs will include blood pressure, respiratory rate, pulse, oxygen saturation, and temperature and will be measured at the times and days shown in the Schedule of Assessments (Table 1).

Vital signs will be measured before any blood draws or injections scheduled for the same time point.

8.2.3.5. Electrocardiograms and Holter Monitoring

At Screening, 12-lead ECGs will be performed in triplicate, with each measurement separated by 2 minutes. The average of the 3 screening ECGs will be used to calculate QTc

and QTcF (Fridericia's formula):
$$QTc = \frac{QT}{\sqrt[3]{RR}}$$

to determine study eligibility. Thereafter, single 12-lead ECGs will be performed at the dates and times indicated in the Schedule of Assessments (Table 1).

On Day 1 of Cycle 1, digital Holter monitoring will be performed from 45 minutes pre-dose through 24 hours post-dose in order to examine any potential QTc changes and relate those, if present, to simultaneously obtained blood samples for plasma drug and/or metabolite concentration determination. ECG extractions of the continuous Holter recordings will be performed at 45, 30, and 15 minutes pre-dose and at specific post-dose time points coinciding with the serial blood sampling time points for PK. Patients will be instructed to assume a supine position 5 to 10 minutes prior to each serial blood sampling time point and remain supine throughout the 5-minute ECG extraction period just prior to serial blood sample collection. During the 24-hour Holter monitoring period, a 12-lead ECG tracing may be printed out at any time while the patient is in the clinic at the discretion of the investigator.

If for any reason Holter monitoring is not performed in conjunction with the PK sampling on Day 1 or the tracings are of poor quality, Holter monitoring may be performed in conjunction with the PK sampling on Day 5.

8.2.3.6. Clinical Laboratory Assessments

All protocol-required laboratory assessments, including hematology (including complete blood count), clinical chemistry (including comprehensive metabolic panel), thyroid panel, coagulation testing, and urinalysis must be conducted in accordance with the Study Procedures Manual and the Schedule of Assessments (Table 1).

Abnormal laboratory tests that are clinically significant should also be recorded as AEs on the CRF, or as medical history if noted during Screening.

A listing of clinical laboratory tests to be performed is provided in Table 6.

Table 6. Listing of Required Screening and Safety Laboratory Parameters

| Laboratory Assessments | Parameters | | |
|------------------------------------|--|---|---|
| Hematology (CBC with differential) | 
 • Hemoglobin • Hematocrit • Platelet count • RBC count • Reticulocytes | 
WBC Count with Differential
 
 • Neutrophils • Lymphocytes • Monocytes • Eosinophils • Basophils | |
| Clinical Chemistry (including CMP) | 
 • Potassium • Sodium • Chloride • Glucose • BUN • Creatinine • Creatinine clearance • ALP | 
 • ALT • AST • GGT • Alkaline phosphatase • Direct bilirubin • Indirect bilirubin • Total bilirubin | 
 • Total protein • Albumin • Calcium • Bicarbonate • Magnesium • Phosphate • Lipase • Amylase |
| Coagulation | 
 • PT | 
 • aPTT | |
| Thyroid Panel | 
 • TSH | 
 • Free T4 | 
 • Free and total T3 |
| Routine Urinalysis | 
 • Color • Turbidity • pH • Specific gravity • Glucose • Ketones | 
 • Nitrites • Bilirubin • Urobilirubin • Protein • RBCs • WBCs | 
 • Epithelial cells • Casts • Crystals • Bacteria • eGFR (Screening only) |
| Other | 
 • Serum or urine hCG pregnancy test (for women of child bearing potential) | 
 • HIV (Screening only) | 
 • Hepatitis A (Screening only) • Hepatitis B (Screening only) • Hepatitis C (Screening only) |

Abbreviations: ALP = alkaline phosphatase; ALT = alanine aminotransferase; aPTT = activated partial thromboplastin time; AST = aspartate aminotransferase; BUN = blood urea nitrogen; CBC = complete blood count; CMP = comprehensive metabolic panel; eGFR = estimated glomerular filtration rate; GGT = gamma glutamyltransferase; hCG = human chorionic gonadotropin; MCH = mean corpuscular hemoglobin; MCV = mean corpuscular volume; PT = prothrombin time; RBC = red blood cell; T3 = triiodothyronine; T4 = thyroxine; TSH = thyroid stimulating hormone; WBC = white blood cell.

8.2.3.7. Ophthalmologic Examinations

Ophthalmologic examinations will be performed by a qualified ophthalmologist at Screening and Follow-up as indicated in the Schedule of Assessments (Table 1). Evaluations will include visual acuity, pupil exam, confrontation visual field, extraocular motility and alignment, interior slit lamp examination, and dilated fundus examination of the retina. Additional ophthalmology evaluations may be requested at any other time, if indicated, as determined by the investigator.

8.3. Pharmacokinetic Assessments

Serial, 3-mL blood (plasma) samples will be taken for PK analysis of CPX-POM and metabolites at the times and days shown in the Schedule of Assessments (Table 1). Each PK sample should be collected as close as possible to the planned time. The actual date and time of each blood sample collection will be recorded. PK samples may not be obtained from the same site where CPX-POM is infused.

Urine samples for PK analysis of CPX-POM and metabolites and measurement of urine volume will be obtained from each patient in urine collection and storage containers. Samples will be collected during Cycle 1 only at the times and days shown in the Study Procedures Manual and the Schedule of Assessments (Table 1). Urine β -glucuronidase activity will be determined in the urine samples collected for PK analysis.

The actual date and time of each sample collection, and the date and time of the previous dose of CPX-POM will be recorded. Processing, storage, and shipping procedures are provided in the Study Procedures Manual.

8.4. Pharmacodynamic Assessments

Serial 7-mL blood samples will be collected to characterize the pharmacologic effects of CPX-POM on circulating biomarkers of Wnt and Notch cell signaling pathways at the times and days shown in the Schedule of Assessments (Table 1). Plasma and peripheral blood mononuclear cells (PBMCs) will be isolated from blood. VEGF, IL-6, and IL-8 concentrations will be measured in plasma by enzyme-linked immunoassay (ELISA). Quantitative Real-Time Polymerase Chain Reaction (qRT-PCR) will be used to characterize gene expression of circulation biomarkers of Wnt and Notch signaling pathways in PBMCs.

The actual date and time of each sample collection and the date and time of the previous dose of CPX-POM will be recorded. Processing, storage, and shipping procedures are provided in the Study Procedures Manual.

9. STATISTICAL CONSIDERATIONS

The statistical analysis plan will be developed and finalized before database lock and will describe the finalized plans for analysis of study data. This section is a summary of the planned statistical analyses at the time of protocol development.

9.1. Number of Patients

The maximum anticipated number of patients in the Single Patient and Standard Dose Escalation Cohorts will be approximately 24. In addition to these estimated 24 patients, Expansion Cohort(s) may also be enrolled after the MTD is reached.

The actual number of patients enrolled will depend on the number of dose escalations and the need to further characterize individual cohorts.

9.2. Analysis Sets

9.2.1. Safety

The **Safety Set** will consist of all patients who receive at least 1 dose of study drug. All safety and PD data will be analyzed using the safety set.

9.2.2. Pharmacokinetics

The **Pharmacokinetic Set** will consist of all patients for whom a plasma and/or urine sample is obtained and analyzed for determination of plasma drug and metabolites concentration.

9.3. Data Handling Conventions

9.4. Demographic Data and Baseline Characteristics

Demographic and baseline measurements will be summarized using standard descriptive methods.

9.5. Safety Analysis

Safety data will be presented in by-patient listings. Categorical safety endpoints will be summarized by frequency of events/abnormalities for each dose group and overall. Continuous safety endpoints will be summarized using descriptive statistics (n, mean, standard deviation, median, Q1, Q3, minimum, maximum) for each dose group and overall.

9.5.1. Determination of Maximum Tolerated Dose

The MTD is defined as the highest dose at which 1 or fewer of up to 6 patients experience a DLT. The MTD will be exceeded if 2 or more patients in a cohort of up to 6 patients experience a DLT. The number and proportion of patients who experience a DLT or Grade 2 or higher AE will be listed and summarized by dose group. A logistic regression will be used to estimate the predicted toxicity probability at each dose level. Details will be provided in the statistical analysis plan.

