| Criteria for Evaluation: | 
Safety:
 
Safety and tolerability will be based on an assessment of AEs, physical examinations, vital signs, electrocardiograms (ECGs), clinical laboratory tests, ophthalmologic assessments, and concomitant medications.
 
The MTD will be defined as the dose BELOW that dose which causes DLTs in $\geq 33\%$ of patients.
 
Pharmacokinetics:
 
Serial blood (plasma) samples and complete urine will be collected over 24-hour periods starting after the first (Day 1) and fifth (Day 5) doses of CPX-POM during Cycle 1 to characterize single dose and steady-state plasma and urine PK of CPX-POM, ciclopirox (CPX), and ciclopirox glucuronide (CPX-G). If patients are unable or unwilling to attend the required 12 hours of clinic visitation required for steady-state PK sampling on Day 5 of Cycle 1, the steady-state PK sampling may be postponed to Day 5 of Cycle 2. Urine β-glucuronidase activity will be measured prior to and after 5 days of CPX-POM administration (i.e., on Days 1 and 5 of Cycle 1).
 
Pharmacodynamics:
 
Blood will be collected to characterize the effects of CPX-POM on circulating biomarkers of Wnt and Notch cell signaling pathways. Plasma and peripheral blood mononuclear cells (PBMCs) will be isolated from blood. Vascular
 |

endothelial growth factor (VEGF), interleukin (IL)-6, and IL-8 concentrations will be measured in plasma by enzyme-linked immunoassay (ELISA). Quantitative real-time polymerase chain reaction (qRT-PCR) will be used to characterize gene expression of circulating biomarkers of Wnt and Notch signaling pathways in PBMCs.

**Statistical
Methods:**

Safety:

Safety data will be presented in by-patient listings. Categorical safety endpoints will be summarized by frequency of events/abnormalities for each dose group and overall. Continuous safety endpoints will be summarized using descriptive statistics (number of subjects [n], mean, standard deviation, median, first quartile [Q1], third quartile [Q3], minimum, maximum) for each dose group and overall.

Pharmacokinetics:

Standard PK parameters will be derived from resultant plasma and urine drug and metabolite concentration-time data using non-parametric methods. PK parameters will be summarized using descriptive statistics.

Pharmacodynamics:

[figure not shown]

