Approximately 24 patients will be enrolled in the Single-Patient and Standard Dose Escalation Cohorts to establish the MTD. In addition to these estimated 24 patients, Expansion Cohort(s) may be enrolled after the MTD is reached to either explore different dosing schedules, increase the experience with a particular tumor type (e.g., muscle invasive

bladder cancer [MIBC]), or to examine the safety and anti-tumor activity of CPX-POM in combination with certain other anticancer agents.

All patients are to attend a Follow-up Visit 28 days (\pm 5 days) after the last study drug dose. No follow-up after completion of the Follow-up Visit is planned, with the exception of monitoring of ongoing treatment-emergent adverse events (AEs) until resolution or until the AE is clearly determined to be due to a patient's stable or chronic condition or intercurrent illness(es).

Dose escalation procedures will be conducted as shown in Table 2. For further details and example doses, see Section 4.2.

Table 2. Dose Escalation Procedures

| Accelerated Titration (Single-Patient Cohorts; n=1 each) | |
|---|---|
| No \geq Grade 2 AEs | 
 Continue evaluation of single-patient dose cohorts. Escalate by 100% to next dose level. |
| At least 1 \geq Grade 2 AE not meeting the definition of DLT | 
 Expand current and subsequent cohorts to at least 3 patients (see Standard Dose Escalation Scheme below). |
| 1 DLT | 
 Expand current cohort up to 6 patients or until 2 DLTs are encountered (Standard Dose Escalation Scheme below). |
| Standard Dose Escalation (Standard Cohorts; n=3 to 6 each) | |
| No DLT | 
 Escalate by 25–50% to next dose level. |
| 1 DLT in \leq 3 patients | 
 Expand cohort up to 6 patients. |
| 1 DLT in 6 patients | 
 Escalate by 25–50% to next dose level. |
| > 1 DLT in \leq 6 patients | 
 MTD reached; stop dose escalation. Possibly explore intermediate doses for the RP2D. |

Abbreviations: AE = adverse event; DLT = dose limiting toxicity; MTD = maximum tolerated dose; RP2D = recommended Phase 2 dose.

A Dose-Limiting Toxicity will be defined as any of the following, if deemed related to study drug:

- Grade 4 thrombocytopenia of any duration
- Grade 3 thrombocytopenia with significant hemorrhage of any duration

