4.2. Planned Doses for Dose Escalation

As described in Sections 4.1, 4.4, and 6.1.4, the starting dose for this study will be 30 mg/m² as a 10-minute IV infusion once daily for 5 days, repeated every 21 days. As stated in Section 4.1, the study will initially adopt an accelerated titration design until \geq Grade 2 toxicity is encountered. Therefore, as an example, if the first \geq Grade 2 toxicity is not seen before the 120 mg/m² dose level in the early cohorts, then the doses shown in Table 3 may be administered.

Table 3. Example Doses for Accelerated Titration Cohorts

| Cohort | Daily Dose (mg/m ²) | Number of Patients |
|--------|---------------------------------|--------------------|
| 1 | 30* | 1 |
| 2 | 60 | 1 |
| 3 | 120 | 1 |
| X | Until \geq Grade 2 toxicity | |

* In the unlikely event of a DLT at this low dose, up to 5 more patients would be accrued at this dose. If >1 DLT was experienced at this dose, a LOWER dose of 15 mg/m² would be explored in a further cohort.

Once \geq Grade 2 toxicity is encountered, the standard dose escalation scheme (“3 + 3”) will apply and dose escalations will proceed in 25 to 50% increments, although these increments may be modified by discussion with the SRC, according to toxicity or other data accrued in preceding cohorts. If, for example, the first \geq Grade 2 toxicity occurs at the 240 mg/m² dose level, the doses shown in Table 4 may be administered. These doses are EXAMPLES and not absolutes until all data from patients in preceding cohorts have been discussed with the Principal Investigators and the SRC. Dose increments generally will be smaller as the MTD is thought to be approaching.

Table 4. Example Doses for Standard Dose Escalation Cohorts

| Cohort | Daily Dose (mg/m ²) | Dose Increase | Number of Patients |
|--------|---------------------------------|---------------|--------------------|
| 4 | 240 | | 3 - 6 |
| 5 | 350 | 46% | 3 - 6 |
| 6 | 475 | 36% | 3 - 6 |
| X | ? 600 | 26% | 3 - 6 |

All SRC discussions and decisions will be documented and patient safety will be the paramount concern.

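### The protocol sets no minimum number of DLT-evaluable patients behind the MTD and does not require the dose below a failing one to be filled, so an MTD can rest on 0/1 or 0/3

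*Protocol*

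**What the plan says.** Establishing the MTD is part of the primary objective (protocol Section 3). The protocol defines it twice. Section 9.5.1 reads "The MTD is defined as the highest dose at which 1 or fewer of up to 6 patients experience a DLT", followed by "The MTD will be exceeded if 2 or more patients in a cohort of up to 6 patients experience a DLT". The synopsis reads "The MTD will be defined as the dose BELOW that dose which causes DLTs in" at least 33% of patients. Neither gives a minimum number of patients at the dose that is named.

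The first phase is described in Table 2 as "Accelerated Titration (Single-Patient Cohorts; n=1 each", with the dose doubling between patients. Section 4.2 says that "the study will initially adopt an accelerated titration design until" a toxicity of Grade 2 or higher appears. From then on the triggering cohort and those after it follow 3+3; earlier single-patient doses do not.

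If the single patient has a DLT, the instruction is "Expand current cohort up to 6 patients or until 2 DLTs are encountered". With more than one DLT in up to six patients it is "MTD reached; stop dose escalation", plus an optional look at intermediate doses for the RP2D. On size, Section 9.1 says: "The maximum anticipated number of patients in the Single Patient and Standard Dose Escalation Cohorts will be approximately 24". It adds that actual numbers will depend partly on a need to characterise individual cohorts further.

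**The concern.** The rules describe in full what happens at the dose that fails and say nothing about the dose beneath it, which is the one that becomes the MTD. If the cohort that triggers the switch to 3+3 is also the one that fails, the dose beneath has been given to a single patient. If a standard cohort passes on 0/3 and the next one fails, the dose beneath has three.

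Section 4.3 says the MTD will inform the dose for future studies. The synopsis sets the dividing line at a 33% DLT rate. One clean patient says almost nothing about which side of that line a dose lies on, and three say little. The plan as written could therefore meet its primary objective with a dose that it has hardly tested.

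**Working it through.** **The planned size.** The figure of about 24 has no derivation to reproduce. Tables 3 and 4 together show three single-patient levels and four cohorts of 3 to 6, so 3 + 4×3 = 15 to 3 + 4×6 = 27. That range contains 24 but does not yield it. Table 4's increments do reproduce: 350/240 − 1 = 45.8%, 475/350 − 1 = 35.7% and 600/475 − 1 = 26.3%, against 46%, 36% and 26% as printed.

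**Tracing the rules on the example doses.**
1. 30, 60 and 120 mg/m²: one patient each, no Grade 2 or higher event.
2. 240 mg/m²: the first patient has a DLT, the cohort expands and a second DLT occurs. Escalation stops.
3. The highest dose with at most one DLT is 120 mg/m², at 0/1. It is also the dose below the failing one, so both definitions agree. The failing dose is twice as high.
4. Patients used: 3 + 2 = 5 to 3 + 6 = 9, of about 24.

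**Exact two-sided 95% upper limits for the DLT rate.** For 0/n the limit is 1 − 0.025^(1/n). For 1/6 it solves (1−p)⁶ + 6p(1−p)⁵ = 0.025.

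| DLTs/n | Upper limit |
|---|---|
| 0/1 | 97.5% |
| 0/3 | 71% |
| 0/6 | 46% |
| 1/6 | 64% |

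**Chance that a dose with true DLT rate p qualifies.**
- One patient: 1 − p.
- Table 2's 3+3 rule: (1−p)³ + 3p(1−p)²·(1−p)³.
- Filled to six (first patient clean, then at most one DLT in five more): (1−p)·[(1−p)⁵ + 5p(1−p)⁴].

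| True rate | One patient | 3+3 | Filled to six |
|---|---|---|---|
| 33% (p = 1/3) | 67% | 43% | 31% |
| 50% | 50% | 17% | 9% |

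**How often this happens.** This part rests on assumed toxicity curves, because the documents give none.

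- *Exact enumeration of Table 2*, with logistic curves in log dose (50% DLT rate at 240, 480 or 960 mg/m², slope 2 or 4) and 40% steps after the switch. A one-patient MTD arises in 65–81% of trials if non-DLT Grade 2 toxicity follows the DLT curve, 39–41% if it appears at half the dose, and 4–17% if it appears at a quarter of the dose.
- *Simulation* on a 30-60-120-240-350-475-600-750-950 ladder, with a DLT rate of 27% at 350 mg/m² and a Grade 2+ rate 1.5 or 2.5 times the DLT rate. A one-patient MTD arises in 34–69% of trials with no background Grade 2 events, 17–27% with 20% background, 7–11% with 40% and 2–4% with 60%.
- *Three or fewer patients.* About 75–90% across the simulations. The enumeration gives 78% (0.038 + 0.739) to 94% (0.813 + 0.126).
- *A one-patient MTD whose true DLT rate is at least one third.* In the enumeration this is 14–22% of trials when Grade 2 toxicity follows the DLT curve, 1–3% at half the dose, and 0.2% or less at a quarter.

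**Room for a floor of six.** On the traced path, filling 120 mg/m² from one to six takes the total to 10–14. In simulation, with the fill moving down a level whenever the filled dose fails, the total stays at or below 24 in 82–100% of trials. A separate set of 18 assumed settings gave a lower end of 76%.

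**The case against.** The strongest reply accepts the trace and disputes its weight.

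*One-patient MTDs may be rare.* Table 2's trigger is any adverse event of Grade 2 or higher, with no relatedness condition, although the text of Section 4.1 speaks of toxicity. Patients with refractory advanced tumours may have such events early, which would end the single-patient phase at a low dose. This stands. A reader might infer that a one-patient MTD is the likely outcome, or that the declared dose would usually be too toxic. The documents support neither: they contain no Grade 2 rate and no toxicity curve, and the range runs from 2 to 81%. The three-or-fewer result does not depend on this in the same way.

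*Six patients do not settle the 33% question either.* Correct: 1/6 has an upper limit of 64%. Six is the size Table 2 already uses for an expanded cohort. It lowers the chance of passing a bad dose but does not exclude one.

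*The plan leaves room.* Section 9.1 allows further characterisation of cohorts, expansion cohorts may follow, and Section 9.5.1 plans a logistic regression of toxicity on dose. A reader might infer that the protocol forbids adding patients at the lower dose; it does not. But these provisions are permissive, expansion comes only after the MTD is reached, and the regression is not tied to naming it. The one explicit step down, to 15 mg/m², applies only if the starting dose fails. The reference to a classical 3+3 does not help, because its rules are written out in Table 2 without this step.

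*The SAP may cover it.* Section 9.5.1 defers details to the SAP, and only its table and listing shells were available. Those contain no DLT or MTD table. One cannot conclude that the SAP text is silent, only that the protocol, which governs escalation, states no floor.

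**Conclusion.** The gap is real and follows from the protocol's text without any assumption: the MTD can be declared on 0/1 or 0/3, with upper limits of 97.5% and 71% for the DLT rate. This is a stated rule that can give an unsound answer to the primary objective (the documents do not call the MTD a primary endpoint). The one-patient case needs the cohort that triggers 3+3, above the starting dose, to fail as well, and its frequency cannot be fixed from the documents. The three-or-fewer case is the ordinary outcome under every curve tried. The limits and qualifying probabilities are exact; the frequencies and the fit within 24 rest on assumed curves, background rates and dose steps.

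**What to change.** Reconcile the synopsis definition, Table 2 and Section 9.5.1 around one stated evidence floor for calling a dose the MTD. An example is six DLT-evaluable patients with at most one DLT. The sponsor and the SRC should decide whether to reach that floor using unused places among the planned 24, and the protocol should say what follows if the dose then fails. Where the floor is not reached, report the dose as *MTD not established*, with its n and exact confidence interval.

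**Cost.** The text change is small. Filling usually takes 3 to 5 more patients and some weeks. It takes more if the filled dose fails and the next one down is also short. For a dose with a true rate of 33% and a clean first patient, that failure has probability 1 − 0.461 = 54%. The total normally, but not always, stays within about 24. The labelling option needs no extra patients.
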